#### 3.2 Patient journey

The patient journey starts when the patient receives a first prescription for one of the index drugs (see table 3). Upon enrolment, patients get access to the MMC. The day of the first prescription is considered T=0.

Medication Management Centre

The MMC will offer patients curated, personalised information regarding DDIs and DDGIs and a patient diary to manage and monitor their drug therapy. Additionally, the MMC will remind the patients by email to complete a questionnaire through the eClinical Data Management Platform Castor These questionnaires collect information on the experience with the MMC, clinical monitoring, clinical outcome, and adverse events, according to the schedule in table 2. Patients can report ADRs in the medication management centre through patient reported outcome measures (PROMs) in the patient diary. More information regarding the MMC can be found in section 5.1.1.

#### • PGx profile

Additionally, the patients in The Netherlands, Greece and Slovenia will donate DNA by a blood sample by a venipuncture or through saliva, and will be genotyped within two weeks for our panel of 26 variants in 4 pharmacogenes (LUMC, UPAT and UL). The results of this PGx test Version number: 6, January 22nd, 2025 16 of 44

will be communicated through the MMC. Patients will be stimulated to share these results with their healthcare providers. This approach is used due to the patient centred nature of our study and MMC approach. Physicians will not receive any specific additional results other than what the patients share with them.

At the end of the 12-week study period, patients will have a semi-structured close out interview with the research nurses regarding the experience of the medication management centre.

• Gene and variant selection

The genes that will be tested are CYP2C19, CYP2C9, CYP2D6 and SLCO1B1 (see also Appendix 3). These all have actionable recommendations in the DPWG guidelines and are related to drugs frequently used in outpatients with polypharmacy. The selection of the genes is based on the drugs that were selected to be index drugs. Additionally, testing these genes is technically feasible and readily implemented in Leiden, Patras and Ljubljana. Updates in the guidelines of the DPWG will be taken into account during the project.

The variants chosen to study align with those studied by the Ubiquitous Pharmacogenomics (U-PGx) consortium. See Appendix 3 for the full pharmacogene and variant panel.

Genotyping

The method used to genotype the variants is up to the recruiting sites themselves. They must meet the following criteria: 1) test for the updated variant panel and 2) participate in proficiency testing programme to ensure quality of genotyping.

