# 3. STUDY DESIGN

## 3.1 Overall study design

This study is a multi-centre, open-label study to assess the impact of the developed MMC in combination with the developed risk score algorithms, patient-reported outcome tool, and model-based precision dosing tool on patient empowerment of polypharmacy patients, thereby improving drug safety. In the study, a total of 120 patients will be enrolled in The Netherlands, Greece, Slovenia, and Germany (30 patients per country). The study subjects will be followed for 12 weeks. At set time intervals (2 and 12 weeks) the subjects will be asked to complete a validated questionnaire through the eClinical Data Management Platform Castor (table 1), for which the patients receive an email and a reminder through the MMC. These questionnaires collect information on the experience with the MMC, clinical monitoring, clinical outcome, and adverse events.

Table 1. Overview of the questionnaires during the 12-week follow-up. The baseline questionnaire comprises of 97 questions, the 2-week questionnaire of 133 questions and the 12-week questionnaire of 206 questions. All questionnaires are adaptive.

	Baseline questionnaire	Adaptive questionnaire in the MMC at time point:	
		2 weeks	12 weeks
Experience			
Usability		Х	х
Health literacy	х		х
Clinical monitoring			
Comorbidities and allergies	х		
Concurrent medication and herbal	х	х	х
remedies (through patient diary)			
Clinical outcome			
Drug adherence	х	Х	х
Quality of Life	х		х
Adverse events			
Patient reported ADR		Х	х
Assessment of ADR severity		х	х
Pharmacogenomics			
DNA sample collection	Х		

The baseline questionnaire will additionally comprise questions covering in- and exclusion criteria, demographics, recruitment information, previous PGx test results, comorbidities and allergies, and the level of health literacy before use of the MMC. In total, the baseline questionnaire consists of 97 questions. The questionnaire offered two weeks after inclusion in the study consists of 133 questions. The last questionnaire, offered 12 weeks after inclusion in the study, consist of 206 questions. All questionnaires are adaptive meaning that the length and duration of the questionnaire depends on the answers of the participants.

[figure not shown]

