Effectiveness in the prevention of ADRs and the ability to identify drug-drug-gene interactions will be explored as a secondary endpoint by comparing results of the pilot study with those obtained from matched historical controls obtained from the control arm of the U-PGx project. This control arm is suitable as historical control group for the EmPaSafe study because of its alignment in key aspects, allowing for meaningful comparisons:

- Genotyped but not empowered with PGx Data: Participants in the U-PGx control arm were genotyped retrospectively, meaning their PGx information was available but not actively utilized in their care. This setup provides a unique baseline to assess the effectiveness of the MMC and the empowerment of EmPaSafe patients with PGx data, as we can analyse whether access to their genetic information and medication adjustments reduces ADRs and improves drug efficacy.
- Comparable Follow-up and Monitoring Protocols: The U-PGx control arm and the EmPaSafe study share similar follow-up methods, including regular monitoring for ADRs and the use of similar questionnaires. This similarity minimizes variation in data collection processes, allowing us to more directly compare ADR prevalence and other outcomes between the two groups.
- Matching for Key Variables: The control group will be matched to EmPaSafe participants based on age, sex, and type and number of medications, controlling for these variables in the analysis. This matching enhances the comparability of the two cohorts and strengthens the reliability of conclusions drawn about the impact of empowering patients with PGx data through the MMC.

Using the U-PGx control arm as a historical comparison thus allows EmPaSafe to evaluate the added value of PGx-informed care without needing a concurrent control group, streamlining the study while leveraging pre-existing data to explore the MMC's role in improving medication safety and personalization.

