# 3.3 Data collection procedures

T=0 is defined as the day the patient initiates the index drug (table 3). During the 12-week follow-up period, the patients will receive surveys at baseline, 2 weeks and 12 weeks and a semi-structured close-out interview at week 12. Patients are requested to complete the surveys within a week. In case a patient discontinues the index drug within the 12-week follow-up period, the follow-up will continue as initially anticipated. The questionnaires will be provided to the patients through the medication management centre.

The data collected by the surveys is summarized in table 2. The MMC will collect: 1) Data entered by patients: demographic information, medical information, symptom diary, 2) Data created by the MMC and its tools: medication plan assessed with its safety risks (DDIs, DGIs, risk score, dosing information) and 3) statistical information collected by the system about the usage of the system by individual patients, sub-cohorts and the whole cohort.

All data will be entered into an electronic Case Report Form (eCRF), which guarantees consistency of data collection procedures. Data will be used exclusively in a pseudonymous fashion and data protection will be guaranteed according to international regulations. Local, independent internal monitors will guarantee data integrity and data homogeneity across all four implementation countries by risk-based monitoring of a random sample of the collected data. The research team will collect and store patient contact information (e-mail address, telephone number, name, and study-ID number) in a separate, local file (national subject identification code list).

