# 5.1.2 Questionnaires

The baseline questionnaire will comprise questions regarding demographics, in- and exclusion criteria, and comorbidities. Additionally, standardized questionnaires will be offered to the patients at 2 and 12 weeks after initiation of the index drug to obtain information about health behaviour, drug use, ADRs (PRO-CTCAE), quality of life (SF-36), MMC experience and health literacy (HLS-EU-Q47). The questionnaires are adaptive meaning that based on the provided answers only relevant follow-up questions will be asked to minimize the burden. Lastly, a semi-structured close-out interview will be held at week 12 to gather information on the experience with the MMC.

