#### 11.2 Recruitment and consent

It is the responsibility of the national Principal Investigators to obtain ethical approval or favourable opinion in writing of the study protocol and protocol amendments, the patient information leaflet, and the informed consent form from the before enrolment of any subject into the study.

Recruitment will differ per site. In the Netherlands, recruitment will involve the LANA pharmacies as well as the outpatient pharmacy of the Leiden University Medical Center (LUMC). All participating pharmacies will receive information about the study during a site initiation visit. Pharmacies will identify eligible polypharmacy patients and pharmacies will identify eligible polypharmacy patients and verbally inform eligible patients about the EmPaSafe study. If patients are interested to participate, the pharmacy will provide the patient information leaflet. Within 2 work days, a researcher from the LUMC will call the patient to provide further information about the study and answer questions. Upon agreement by the patient, an ICF will be provided. The patient inclusion will be managed by the LUMC research team. The study team is also available for any questions both during recruitment and throughout the study.

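### Many ADEs reported at week 2 precede any PGx-driven change in care, yet they enter an unwindowed total used to judge what PGx adds

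*Protocol*

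**What the plan says.** **Purpose of the comparison.** Protocol section 3.1 compares the study cohort with matched controls from the U-PGx control arm, who were genotyped but whose results were not used in their care. It says that "we can analyse whether access to their genetic information and medication adjustments reduces ADRs and improves drug efficacy". It closes by presenting the comparison as a way to measure what PGx-guided care adds. Sections 2.2 and 8.1.2 put the ADE question more broadly, as the effect of bringing the MMC into healthcare.

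**Route and timing of the PGx result.** Under section 3.2, patients outside Germany "will be genotyped within two weeks for our panel of 26 variants in 4 pharmacogenes". Results are shown to the patient in the MMC. "Physicians will not receive any specific additional results other than what the patients share with them".

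**Clock.** Section 3.3 sets T=0 at the start of the index drug; section 3.2 sets it at the first prescription. In the Netherlands enrolment follows the prescription: "Within 2 work days, a researcher from the LUMC will call the patient" (section 11.2), and the consent form comes after that call.

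**ADR collection.** Table 1 in section 3.1 marks patient-reported ADRs at 2 and 12 weeks. The week-2 point has two anchors. Section 3.1 has "The questionnaire offered two weeks after inclusion in the study consists of 133 questions", whereas section 5.1.2 has "standardized questionnaires will be offered to the patients at 2 and 12 weeks after initiation of the index drug".

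**Outcome.** The secondary clinical outcomes in section 8.1.2 include a total ADE count for the index and later drugs. No start date or post-result window is attached to it.

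**The concern.** For PGx to change an ADE in this study, a sample must be taken and genotyped, the result must appear in the MMC, the patient must pass it on, and a prescriber must act on it. The ceiling for genotyping alone equals the time to the first ADR questionnaire. Events from the opening weeks of a new drug therefore enter the comparison although PGx had little or no opportunity to influence them.

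Two errors of interpretation can follow. First, a real PGx effect is diluted towards no difference. Second, the controls are historical and matched only on age, sex and type and number of medications. A difference between the cohorts that already existed before any result was released would sit inside the same total and could be read as a benefit or harm of PGx. A single total cannot separate these; a split by period would help.

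**Working it through.** The protocol gives no ADE rate, effect size or power figure to reproduce. Its only relevant arithmetic agrees: 4 sites × 30 = 120 patients, of whom 3 × 30 = 90 are genotyped (sections 4.1 and 8.2).

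**Step 1: timeline.** Let *d* be the delay from T=0 to sampling and *g* the genotyping time, with *g* ≤ 2 weeks. I assume *g* runs from sampling, because the protocol names no start point. The result is available at *d* + *g* at the earliest.
- Week-2 questionnaire counted from drug start: at *g* = 2 the result arrives at week 2 + *d*, at or after the questionnaire date.
- Counted from inclusion, with sampling at inclusion: at *g* = 2 the result arrives on the questionnaire date, and the period asked about covers *d* + 2 weeks on the drug.

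Under either anchor, at the maximum turnaround no event before the two-week point follows a PGx result. With a shorter *g*, part of the period follows the result, but sharing and a prescribing decision are still needed before care can change.

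**Step 2: follow-up time without a result.** Share = lag / 12, in the 90 genotyped patients (90 × 12 = 1080 person-weeks).

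| Lag from T=0 | Person-weeks without result | Share |
|---|---|---|
| 1 week | 90 | 8.3% |
| 2 weeks | 180 | 16.7% |
| 3 weeks (late sampling or release, assumed) | 270 | 25% |

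**Step 3: dilution.** Let *f* be the share of expected ADEs that falls before the result, and RR_post the true rate ratio afterwards. The early ratio is set to 1 to isolate the PGx component.

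Observed RR = *f* + (1 − *f*) × RR_post

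| *f* (assumed) | RR_post = 0.70 | RR_post = 0.80 |
|---|---|---|
| 1/6 (even spread, 2 of 12 weeks) | 0.75 | 0.83 |
| 0.30 | 0.79 | 0.86 |
| 0.50 | 0.85 | 0.90 |

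For example, 1/6 + 5/6 × 0.70 = 0.167 + 0.583 = 0.75, and 0.50 + 0.50 × 0.70 = 0.85.

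**Step 4: the German patients.** They receive no PGx testing. If they were pooled into a PGx contrast, with equal ADE rates across sites and no PGx effect in Germany (both assumed), the 0.75 would become 0.75 × 0.75 + 0.25 × 1 = 0.81. Even with no lag, 0.70 would become 0.75 × 0.70 + 0.25 = 0.775. In these examples pooling moves the ratio about as much as or more than the lag does with evenly spread ADEs, so a PGx statement should be limited to the genotyped sites.

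**The case against.** **The two weeks are a ceiling.** A reader might infer that every week-2 ADR occurs without PGx information. The documents do not support that: they give no minimum or typical turnaround, and an early result leaves part of the period exposed. This stands. The claim is certain only at or near the maximum.

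**The week-2 contrast might look like a clean negative control.** It is not. Section 3.2 gives patients MMC access on enrolment, including drug-interaction information, so a real intervention effect may already be present at week 2. This stands too.

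**The ADE objective covers the MMC as a whole.** Sections 2.2 and 8.1.2 support this. For a strategy delivered from the start, waiting for the genotype is part of the strategy, and counting every ADE is legitimate. Only the PGx-specific reading in section 3.1 is affected.

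**Windows belong in the statistical analysis plan.** That plan is not at hand and may define one, so the absence of a window is not in itself a defect. Two things remain. Section 3.1 already fixes a PGx interpretation. And section 3.3 does not name the date of result release among the data collected; MMC usage records may hold it, but an analysis plan cannot recover a date that was never kept.

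**The comparison is exploratory.** Sections 4.4 and 10.2 make it unpowered and descriptive. That limits severity, although section 4.4 also intends the results to inform a larger study, for which a diluted or misattributed effect would be a poor guide.

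**The controls may lack week-2 data.** The protocol describes the U-PGx follow-up and questionnaires only as similar. The split therefore depends on a schedule that the protocol does not give.

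**Conclusion.** The point holds in a limited form. The protocol's own timeline places many week-2 ADEs before any PGx-driven change in care, and an unwindowed total would mix them into a comparison that section 3.1 reads as evidence on PGx. At the maximum turnaround with sampling at T=0, one sixth of follow-up has no result. An assumed true ratio of 0.70 would then appear as 0.75 to 0.85 for *f* between 1/6 and 0.50. Neither *f* nor the ratio comes from the documents; an *f* above 1/6 requires ADEs to cluster early after starting a drug, for which the protocol gives no figure.

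Dilution runs towards no difference. A pre-existing cohort difference could run either way, but that is a general weakness of historical controls, which the genotyping lag does not create; the split only makes it easier to see. The total ADE count remains valid for the MMC strategy as a whole. Severity is low because the comparison is secondary, descriptive and unpowered. The change is still worth making because it is cheap.

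**What to change.** 1. Keep the total ADE count as the outcome for the whole MMC strategy.
2. Also report ADEs for weeks 0-2 and weeks 2-12 separately, with identical windows in the matched controls where the U-PGx data allow. Do not drop early events from the study cohort alone, which would create a new bias.
3. Base any PGx-specific statement on weeks 2-12 in the genotyped patients (Netherlands, Greece, Slovenia) and their matched controls.
4. Present the week-2 contrast as an informative but imperfect check on comparability, and say that MMC drug-interaction information is already active by then.
5. Record, for each patient, the date the PGx result becomes visible in the MMC.
6. Reconcile the week-2 anchor between sections 3.1 (inclusion) and 5.1.2 (start of the index drug), together with the two statements of T=0 in sections 3.2 and 3.3.

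**Cost.** One extra date field, fewer events in the PGx contrast, and dependence on the controls' questionnaire schedule, which should be checked before the split is promised. No new patient contact is needed, because the two questionnaires are already separate.

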# 3.3 Data collection procedures

T=0 is defined as the day the patient initiates the index drug (table 3). During the 12-week follow-up period, the patients will receive surveys at baseline, 2 weeks and 12 weeks and a semi-structured close-out interview at week 12. Patients are requested to complete the surveys within a week. In case a patient discontinues the index drug within the 12-week follow-up period, the follow-up will continue as initially anticipated. The questionnaires will be provided to the patients through the medication management centre.

The data collected by the surveys is summarized in table 2. The MMC will collect: 1) Data entered by patients: demographic information, medical information, symptom diary, 2) Data created by the MMC and its tools: medication plan assessed with its safety risks (DDIs, DGIs, risk score, dosing information) and 3) statistical information collected by the system about the usage of the system by individual patients, sub-cohorts and the whole cohort.

All data will be entered into an electronic Case Report Form (eCRF), which guarantees consistency of data collection procedures. Data will be used exclusively in a pseudonymous fashion and data protection will be guaranteed according to international regulations. Local, independent internal monitors will guarantee data integrity and data homogeneity across all four implementation countries by risk-based monitoring of a random sample of the collected data. The research team will collect and store patient contact information (e-mail address, telephone number, name, and study-ID number) in a separate, local file (national subject identification code list).

# 4. STUDY POPULATION

# 4.1 Population (base)

Polypharmacy patients of any ethnicity, which are over 18 years of age and within routine care receiving a first prescription for one of the index drugs (see table 3), are eligible to participate in the study. The participating centres will **focus on, but are not limited to**, recruiting within a specific therapeutic area that cover both in- and outpatient settings (see table 2). This diverse population is a reflection of the general polypharmacy population which allows us to assess the use of the MMC in this diverse and heterogenous group of patients.

Table 2. Centres participating to the study, with corresponding recruitment of patients. The centres are not limited to recruiting patients within these specific therapeutic areas and can also include patients outside them.

Site	Therapeutic focus for treatment	Number of patients in- cluded in total	Country/ Language
LUMC	Leiden University Medical Centre will in-	30	The Netherlands/
	volve community pharmacies in Leiden to		Dutch
	recruit patients.		
UPAT	Psychiatric patients will be recruited from	30	Greece/
	the psychiatric clinic of the General Uni-		Greek
	versity Hospital of Patras.		
UL	Primary care patients will be recruited	30	Slovenia/
	from three primary health care centres		Slovenian
	(Community Health Centre Ljubljana,		
	Family Medicine Clinic KUS and Health		
	Institute Zdravje)		
UKA	Polypharmacy patients from different	30	Germany/
	fields of medicine, above 60 years of age		German
	will be recruited in UKA's outpatient unit		
	for clinical pharmacology.		
Total for	study	120	

# 4.2 Inclusion criteria

In order to be eligible to participate in this study, a subject must meet all of the following criteria:

- Polypharmacy defined as the use of 5 or more drugs
- Start usage of at least one index drug according to the list in table 3. See Appendix 4.
- Subject must be ≥ 18 years old
- Subject is able and willing to take part and be followed-up for at least 12 weeks
- Subject is able to donate blood or saliva
- Subject has signed informed consent

Table 3. List of index drugs eligible for inclusion, based on their presence in the U-PGx cohort. For all these drug-gene combinations, an actionable DPWG guideline is available. See also Appendix 4.

Drug name	Gene
Amitriptyline	CYP2D6
Atorvastatin	SLCO1B1
Citalopram	CYP2C19
Codeine	CYP2D6
Escitalopram	CYP2C19
Paroxetine	CYP2C9
Sertraline	CYP2C19
Simvastatin	SLCO1B1
Tramadol	CYP2D6
Venlafaxine	CYP2D6

### 4.3 Exclusion criteria

A potential subject who meets any of the following criteria will be excluded from participation

in this study:

- Pregnancy or lactating
- Life expectancy estimated to be less than three months by treating clinical team
- Unable to consent to the study
- Unwilling to take part
- Subject has no fixed address
- Subject has previously been genotyped for PGx genes
- Subject has no current general practitioner
- Subject is, in the opinion of the Investigator, not suitable to participate in the study
- Estimated glomerular filtration rate (MDRD) of less than 15 ml/min per 1,73m2
- Patients with advanced liver failure (stage Child-Pugh C)

